1. BACKGROUND

1.1 Study Disease(s)

Somali women have one of the highest rates of cervical cancer in the world (24 cases annually per 100,000).^{1,2} Nearly all cervical cancers can be prevented by identifying and removing pre-cancerous lesions caused by high-risk human papillomavirus (HPV). In the U.S. the proportion of Somali immigrant women who are up-to-date with guideline-recommended cervical cancer screening ranges from 25%-50%,³⁻⁵ compared with 82% for the U.S. general female population.⁶ Low screening rates contribute to increases in cervical cancer incidence, late-stage diagnoses, treatment burden, and mortality.⁷⁻⁹ These prevention disparities are caused by a range of factors, including health literacy challenges,¹⁰ limited awareness about HPV and cervical cancer,¹¹⁻¹⁵ reluctance to use preventive health care due to misperceptions about health care costs (even with insurance coverage),¹⁰ cultural or religious beliefs,^{12,16-18} and patient concerns related to modesty.¹⁴ Additionally, health care providers do not always feel skilled or confident to provide Pap tests on circumcised Somali women.¹⁹⁻²¹ Physical barriers in circumcised women can also lead to poor access for conducting accurate cervical examinations,²² which can reduce provider confidence.²³

1.2 Rationale

The U.S. Preventive Services Task Force (USPSTF) guidelines include HPV testing alone (primary HPV screening) as a recommended cervical cancer screening strategy in women aged 30-65 years.²⁴ With primary HPV screening *self-screening is an emerging option*, because HPV tests (unlike Pap tests) can be performed on self-collected samples. HPV self-sampling is accurate for detecting precancerous cervical lesions,²⁵ and effective in reaching women who otherwise delay or opt out of screening,²⁶⁻²⁸ including Somali immigrant women.²⁹ While research in this area has focused primarily on home-based, mail-in self-sampling kits,^{26-28,30} there is an untapped opportunity to utilize HPV self-sampling in primary care settings. Offering HPV self-sampling in primary care could effectively increase cervical cancer screening rates in Somali women by positioning providers to address screening barriers,³¹ enabling clinics to opportunistically fit in HPV self-sampling with other appointments, and providing an alternative modality for circumcised women.³²

2. OBJECTIVES

2.1 Aim 1

Utilizing the Consolidated Framework for Implementation Research (CFIR) and Social Cognitive Theory (SCT), identify patient-, provider-, clinic-, and systems-level barriers and facilitators to inform refinement of implementation strategies to promote Somali women's uptake of HPV self-sampling.

2.2 Aim 2 (primary objective)

Using a difference-in-difference design to compare between-period changes in Somali women attending intervention (clinics implementing the HPV self-sampling option as standard of care) versus control primary care clinics, assess the effect of implementing HPV self-sampling on women's completion of cervical cancer screening.

2.2.1 Aim 2 (secondary objective)

Assess the effects of implementing HPV self-sampling on cervical cancer screening uptake in all patients.

2.3 Aim 3

Utilizing mixed methods and the Reach Effectiveness Adoption Implementation Maintenance framework (RE-AIM), assess the HPV self-sampling implementation strategies used by the clinics and develop a comprehensive implementation science based framework of the processes and strategies needed to implement HPV self-sampling in primary care for Somali patients and all other patients.

3. PATIENT SELECTION

3.1 Inclusion Criteria

3.1.1 Aim 1

Focus groups:

- (a) Identify as a Somali woman
- (b) Between ages of 30-65 years and eligible for cervical cancer screening

Clinic interviews:

- (a) Administrators, physicians, nurses, interpreters, community health workers (CHWs), and medical assistants (MAs), employed at intervention clinics

3.1.2 Aim 2

Primary objective:

- (a) Identify as a Somali woman
- (b) Between ages of 30-65 years
- (c) Due or overdue for routine cervical cancer screening
- (d) Receiving care at intervention clinics (MHealth Fairview Smiley's Family Medicine clinic, Community-University Health Care Center (CUHCC), or People's Center Clinics and Services) or control clinics (across the MHealth Fairview system)

Secondary objective:

- (a) Between ages of 30-65 years
- (b) Due or overdue for routine cervical cancer screening
- (c) Receiving care at intervention clinics (MHealth Fairview Smiley's Family Medicine clinic, Community-University Health Care Center (CUHCC), or People's Center Clinics and Services) or control clinics (across the MHealth Fairview system)

3.1.3 Aim 3

Patient interviews:

- (
 - (a) Between ages of 30-65 years
 - (b) Participated in HPV self-sampling for cervical cancer screening at an intervention clinic

Clinic interviews:

- (a) Administrators, physicians, nurses, interpreters, CHWs, and MAs, employed at intervention clinics

3.2 Exclusion Criteria

3.2.1 Aim 1

- (a) Focus groups: None
- (b) Clinic interviews: None

3.2.2 Aim 2

- (a) Opted out of research in the electronic health record

3.2.3 Aim 3

- (a) Patient interviews: None
- (b) Clinic interviews: None

3.3 Inclusion of Women and Minorities

3.3.1 Aim 1

Focus groups:

The goal of the focus groups is to assess barriers and facilitators to inform refinement of implementation strategies to promote Somali women's uptake of HPV self-sampling, so participants will be restricted to female sex Somali individuals who meet our study eligibility requirements. Non-English speaking participants will be included, specifically Somali speakers.

Clinic interviews:

Clinic interviews will be restricted to administrators, physicians, nurses, interpreters, CHWs, and MAs, employed at intervention clinics. The ethnic/racial composition will largely reflect the ethnic/racial composition of the employees at each clinic.

3.3.2 Aim 2

Primary objective:

The goal of the primary objective is whether in-clinic HPV self-sampling improves cervical cancer screening completion among Somali women. Because cervical cancer only affects people with a uterine cervix, the study population will be composed of female sex Somali individuals who meet our study eligibility requirements.

Secondary objective:

The goal of the secondary objective is whether in-clinic HPV sampling improves cervical cancer screening completion among all patients. Because cervical cancer only affects people with a uterine cervix, the study population will be composed of female sex individuals who meet our study eligibility requirements. Race and ethnicity are not eligibility requirements for participation, so the ethnic/racial composition of our study population will largely reflect the ethnic/racial composition of female patients of M Health Fairview, CUHCC, and People's Center Clinics and Services.

3.3.3 Aim 3

Patient Interviews:

The goal of the patient interviews is to assess the HPV self-sampling implementation strategies used by the clinics and develop a comprehensive implementation science based framework of the processes and strategies needed to implement HPV self-sampling in primary care for both Somali patients and all other patients, so participants

will include female sex individuals who meet our study eligibility requirements. Non-English speaking participants will be included, specifically Somali speakers as this study is targeting Somali women.

Clinic interviews:

Clinic interviews will be restricted to administrators, physicians, nurses, interpreters, CHWs, and MAs, employed at intervention clinics. The ethnic/racial composition will largely reflect the ethnic/racial composition of the employees at each clinic.

3.4 Inclusion of Children

3.4.1 Aim 1

Focus groups:

We are not enrolling individuals younger than age 30. As of 2022, USPSTF cervical cancer screening guidelines⁹ recommend primary HPV screening commence at age 30 years .

Clinic interviews:

All health professionals are adults; as such, children will not be included in this study aim.

3.4.2 Aim 2

We are not enrolling individuals younger than age 30. As of 2022, USPSTF cervical cancer screening guidelines⁹ recommend primary HPV screening commence at age 30 years.

3.4.3 Aim 3

Patient interviews:

We are not enrolling individuals younger than age 30. As of 2022, USPSTF cervical cancer screening guidelines⁹ recommend primary HPV screening commence at age 30 years.

Clinic interviews:

All health professionals are adults; as such, children will not be included in this study aim.

4. STUDY PROCEDURES

4.1 Subject Recruitment and Screening

4.1.1 Aim 1

Focus groups:

Focus group participants will be recruited from partnering clinics and in the community through local mosques or community organizations.

Clinic recruitment at each intervention clinic may happen in several ways: a) clinic staff mentioning the study and providing recruitment flyers at the clinic for distribution, b) the bilingual research facilitator tabling in the clinic lobby with recruitment flyers, and c) community outreach through contacts at local mosques and community organizations connected to the Somali community

Participants will be screened for eligibility and provided the information sheet about the study either in person (if recruitment is in person at the clinic or community site) or

remotely. In the case of remote screening and consenting, the process will occur over the phone or Zoom; the information sheet will be sent by email or a link provided over Zoom. After being screened and consenting to participate, participants can select if they prefer to participate in a focus group conducted in either English or Somali, choose a focus groups time/date and format (virtual or in-person) and will fill out a demographic survey over phone with the research facilitator or through a Qualtrics or REDCap link sent via text or email.

Clinic interviews:

Administrators, physicians, nurses, interpreters, CHWs and MAs will be recruited at each clinic by working with clinic leadership to identify potential participants. All potential participants will be clearly informed that participation is voluntary and will not affect their position at the clinic. The goal will be to recruit 15 participants at each clinic.

4.1.2 Aim 2

Unless patients indicated in the medical record that they do not wish to have their records used for research purposes, under a waiver of consent and HIPAA authorization inclusion and exclusion criteria data will be programmatically extracted from the EHR in both intervention and control clinics (age, history of sub-cervical hysterectomy, cervical cancer screening / diagnostic / treatment history and results, etc.).

4.1.3 Aim 3

Patient interviews:

Patients who complete the self-sampling option will be given study contact information by the clinic (by flyer, verbally or mailed letter) so they can reach out to the study team if they would like to participate in a short interview.

Clinic interviews:

Administrators, physicians, nurses, interpreters, CHWs and MAs will be recruited at each clinic by working with clinic leadership to identify potential participants. All potential participants will be clearly informed that participation is voluntary and will not affect their position at the clinic. The goal will be to recruit 10 participants at each clinic.

4.2 Procedures

4.2.1 Study Design

Aim 1

Patient focus groups, and individual provider or clinic staff interviews will be conducted.

Aim 2

Three primary care clinics (M Health Fairview Clinic - Smiley's, Community-University Health Care Center (CUHCC) and People's Center Clinics & Services) will implement HPV self-sampling as part of standard care for cervical cancer screening for all patients.

Programmatically extracted data from these clinics will be compared to cervical cancer screening rates in M Health system clinics that do not implement HPV self-sampling.

Aim 3

Patient 1:1 interviews, and individual provider or clinic staff interviews will be conducted.

4.2.2 Study Procedures

Aim 1:

Patient focus groups and individual provider or clinic staff interviews will be conducted.

Focus groups (n=40 – 80 participants):

We will collect focus group data from Somali women, between 30-65 years of age. The age range reflects the current guidelines for women who should receive cervical cancer screening with primary HPV testing. Five to eight focus groups (up to 10 participants each) will be conducted with Somali women.

Focus groups will be conducted in two parts.

- First, we will ask about knowledge about HPV and cervical cancer, screening experiences and views on HPV self-sampling, what influences their decision making about screening, and their experience with clinic providers.
- During the second part of the focus groups, we will provide brief information on HPV self-sampling to help inform the discussion. Participants will be asked their views on how self-sampling could best be implemented in primary care, including their perspectives on barriers and facilitators, informational needs, tailoring of instructions, and how it would best fit in the clinic visit.

Participants will receive \$50 for participating. The focus groups will last approximately 90 minutes.

Focus groups will be held either in a virtual format or in one of the following venues: (1) at MHealth Fairview Smiley's Family Medicine Clinic or the People's Center in a private room (hereafter referred to as partner clinics); (2) a private room at a community center or mosque. Some participants might feel more comfortable in a remote format versus in-person setting and vice versa.

Clinic interviews (n=30)

We will collect interview data from 30 individual provider or clinic staff, including physicians, nurses, interpreters, CHWs, and medical assistants (MAs). Each interview is estimated to take between 30-45 minutes. The interview guide will include views on HPV self-sampling in the context of primary care, views on Somali women's needs and resources about cervical cancer screening and HPV self-sampling (e.g., patient education needs), the role of staffing, workflow, current protocols, knowledge and beliefs about HPV self-sampling, how individuals anticipate the best processes for approaching implementation and demographic questions.

Data from focus groups and interviews will inform implementation strategies to promote uptake of HPV self-sampling in primary care for Somali women.

Aim 2:

Three primary care clinics (M Health Fairview Clinic - Smiley's, Community-University Health Care Center (CUHCC) and People's Center Clinics & Services) will implement HPV self-sampling as part of standard routine care for cervical cancer screening for all patients, as a new usual care option for cervical cancer screening.

The study team will support the clinics in the implementation process as part of a quality improvement initiative. Findings from Aim 1 will be used to guide the development of the self-sampling components, including refinement of existing self-sampling instructions, the creation of new culturally tailored patient information materials, training materials for providers, workflow guidance, referral processes, and guidance on reporting and communication.

Data collection: Demographics, provider and patient characteristics, healthcare utilization (whether HPV self-sampling offered/completed, questions, or problems patients may have had with HPV self-sampling, screening history, gravidity/parity, receipt of preventative services like mammography or colorectal screening, etc.), health information (e.g. circumcision status, BMI, co-morbidity index, etc.), screening utilization, Pap and HPV test results, coloscopies, biopsy results (to identify CIN 2+ cases), and CIN 2+ treatment will be programmatically extracted from the EHR (in both intervention and control clinics).

Control clinics: All other M Health Fairview primary care clinics in the metro area will be included as control clinics. Control clinics will have passive participation and their only involvement will be that data will be pulled from these clinics from the M Health Fairview research data warehouse.

Aim 3:

We will ask patients who participated in the self-sampling, and administrators, physicians, nurses, interpreters, MAs, and CHWs at each participating clinic, to identify their experience of implementation. We will use these data to identify barriers and facilitators for implementing HPV self-sampling, and needs for ongoing sustainability. Participants who were included in Part 1 can also be included in Aim 3.

Patient interviews (n=30):

Patients who did the self-sampling option will be interviewed throughout the study implementation phase. Interviews will explore views on HPV self-sampling and demographic questions. In addition, women with abnormal results will be asked about their experience and of the resultant care. The sample will be a convenience sample, recruited throughout the study. Participating clinics will provide patients who do self-sampling the contact information for study staff and instructions of how to get in touch if interested in participating in the follow-up interview.

Clinic interviews (n=30):

The participants will include administrators, physicians, nurses, interpreters, CHWs and MAs. The semi-structured interview guide will explore provider and staff perspectives on the reach of HPV self-sampling in the clinic, the perceived effectiveness of the HPV self-sampling intervention, the adoption of HPV self-sampling across the clinic, including barriers and facilitators to provider practice, views on the self-sampling implementation strategies used, and provider views on the ongoing maintenance of self-sampling, including intention to continue to implement the strategy, and what resources –

financial, training or staff related – would be needed to ensure successful ongoing delivery. Demographic information from interviewees will also be collected. Interviews are expected to take around 30 minutes in length, and will be audio recorded.

4.3 Early Termination

Subjects will not be terminated from the study by the study investigators; however, subjects may choose to decline some or all study procedures. All subject withdrawals will be documented.

5. STATISTICAL CONSIDERATIONS

5.1 Power Analysis

For our primary outcome analysis (Aim 2), we expect to enroll 1,130 Somali patients in each of the pre- and post-intervention cohorts divided between the three intervention clinics and 4,550 Somali patients in each of the pre- and post-intervention period cohorts in the control clinics. Preliminary data from the two intervention clinics suggests that 15% of Somali patients in the pre-intervention cohort will be screened during the study period, and a somewhat lower screening rate of 11% in the control clinics. Based on results from our prior HOME trial in underscreened women,³⁰ we assume the screening rate in the intervention clinics will increase by at least 9% (from 15% to 24%) in the post-intervention period and will not change in the control clinics. Assuming accrual and screening times are uniformly distributed over the study periods, we estimate 98% power to detect an effect of the intervention in the difference-in-difference analysis. We will still have 80% power if the intervention increases the rate of screening by only 6% (from 15% to 21%). These power calculations are conservative in that they are based on an assumption of independent data, and we expect some overlap between the pre- and post-intervention cohorts in each clinic, and additional intervention clinic (CUHCC). The induced correlation will increase study power since the contrast of interest will be between correlated observations.

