The primary outcome of screening completion is defined as either: a) receiving Pap and/or HPV testing by a clinician, or b) self-sampling HPV-negative or HPV16/18+; or c) self-sampling positive for other HR-HPV types or unsatisfactory, and returning for a follow-up Pap test to complete the screening episode. For individuals with other HR-HPV or unsatisfactory test results on self-sampling, a follow-up Pap test is required. Therefore, our criterion specifies that if the Pap test is not completed, the individual will not be considered completely screened. Individuals who initiate screening during the 12-month pre- or post-intervention period are allowed up to 3 months after the screening initiation date to complete the screening episode, if necessary (e.g., returning for a follow-up Pap test after self-sampling positive for other HR-HPV types or unsatisfactory). Analyses will model time to initiating a completed screening episode.

To analyze the data using a difference-in-difference approach, we will fit a Cox proportional hazards model with time to initiating a completed screening episode as the outcome, $\lambda(t \mid X_i, W_i, Z_i) = \lambda(t) \exp\{\beta_1 X_i + \beta_2 W_i + \beta_3 X_i W_i + \beta_4 Z_i + \beta_5 Z_i W_i\}$, where $\lambda(t)$ is the baseline hazard function indexed by time on study in the pre- or post-intervention study period, X_i is an indicator of

pre-intervention ($X_i=0$) or post-intervention ($X_i=1$) cohort, W_i is an indicator of study ($W_i=0$) or control ($W_i=1$) clinic, and Z_i is a vector that includes adjustment for patient covariates, e.g., age, time since last cervical screen. We will use robust standard errors to account for correlation between observations in the pre- and post-intervention cohorts (i.e., women who are due for screening during the pre-intervention period and are seen again in the post-intervention period prior to being screened). A similar model will be used for the secondary outcome of screening initiation, and for the secondary objective these analyses will be applied to the larger cohort of all women (not just Somali-American women).

We will report the proportions completing necessary in-clinic follow-up within 3 months after an abnormal kit result by screening history, and we will summarize the numbers of women that opt for clinician-administered, self-sampling, and no screening in the intervention group (primary: Somali-American women, secondary: all women)

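### The primary model leaves out clinic although three clinics carry the intervention, and the claim that the stated power is conservative is not supported

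*Combined protocol and SAP*

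**What the plan says.** Section 5.1 (Power Analysis) expects 1,130 Somali patients "in each of the pre- and post-intervention cohorts divided between the three intervention clinics" and 4,550 per period in the control clinics. Screening is assumed to be 15% before the intervention in the intervention clinics and 11% in the control clinics in both periods. Stated power is 98% for a rise to 24% and 80% for a rise to 21%. The section continues: "These power calculations are conservative in that they are based on an assumption of independent data". It gives two reasons. The first is that "we expect some overlap between the pre- and post-intervention cohorts in each clinic", from which it concludes: "The induced correlation will increase study power since the contrast of interest will be between correlated observations". The second is an extra intervention clinic, CUHCC. The preliminary rates come from fewer sites: "Preliminary data from the two intervention clinics suggests that 15% of Somali patients".

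Section 5.3.2 (Analysis plan relevant to Aim 2) fits a Cox model with period, study or control clinic, their interaction, patient covariates and covariate-by-group terms. It has no term for the individual clinic. On dependence it says: "We will use robust standard errors to account for correlation between observations in the pre- and post-intervention cohorts", and identifies those observations as "women who are due for screening during the pre-intervention period and are seen again in the post-intervention period prior to being screened".

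**The concern.** The intervention is introduced clinic by clinic (sections 4.2.1 and 4.2.2), so the effect estimate rests on the pre-to-post change in three clinics. Such changes can differ between clinics for reasons unrelated to self-sampling, such as staffing, outreach or data capture. The planned standard errors do not allow for this, so a positive result could look more certain than it is.

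The power section names only the dependence that helps, repeat women, and not the dependence that hurts, clinic-level change. A reader is left to think that true power exceeds 98% and 80%. The help from repeat women is also doubtful. By the plan's own description they were not yet screened when seen again, so their pre-period value of the primary outcome is always no event, and there is little for pairing to exploit.

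**Working it through.** **Inputs from section 5.1.** Events are 1,130 × 0.15 = 169.5 (intervention, pre); 1,130 × 0.24 = 271.2 or 1,130 × 0.21 = 237.3 (intervention, post); and 4,550 × 0.11 = 500.5 (control, each period). Alpha is not stated; two-sided 0.05 is assumed.

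**1. Reproducing the plan's figures.** On the log rate-ratio scale, v = 1/169.5 + 1/e + 2/500.5, where e is the post-period intervention events, and power = Φ(b/√v − 1.96).
- 24%: v = 0.01358, b = ln(24/15) = 0.470, b/√v = 4.033, power 98.1%.
- 21%: v = 0.01411, b = ln(21/15) = 0.336, b/√v = 2.833, power 80.9%.

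Both agree with the stated figures.

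**2. What overlap can add.** The documents give neither the overlap fraction nor the heterogeneity between women, so both were varied. In a simulation in which 90% of unscreened women return and the person-level log-hazard SD runs from 0 to 3.0, the pre/post correlation is 0.00 to 0.08 and the variance ratio 1.00 to 0.92. Power at +6 points is then 80.7% to 84.0%, against 80.9%. In a boundary case (all unscreened women return, and every woman who can be screened is screened by the end of the post-period), the ratio is 0.89: 0.336/√(0.89 × 0.01411) − 1.96 = 1.04, or 85.1%. At +9 points that case gives 98.9%. A separate simulation with gamma frailty found correlations of at most about 0.08 (intervention) and 0.03 (control), giving at most 83.4% and 98.6%.

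**3. Type I error of the planned test.** Let s be the SD between clinics of the pre-to-post change in log rate. At s = 0.10, one SD takes a 15% clinic to 0.15 × exp(±0.10), about 13.6% to 16.6%, with no intervention effect. With three equal intervention clinics and K equal control clinics (K = 10, 20, 40 assumed), the true variance under no effect is v0 + s²(1/3 + 1/K), where v0 = 2/169.5 + 2/500.5 = 0.01580. The planned test uses v0 alone, so its type I error is 2[1 − Φ(1.96√(v0/(v0 + s²(1/3 + 1/K))))].
- s = 0.05: 5.7-5.8%
- s = 0.10: 7.7-8.3% (K = 20: 1.96 × √(0.01580/0.01963) = 1.758, or 7.9%)
- s = 0.20: 15.6-17.6%

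A clinic-level Poisson simulation (40,000 runs per setting) gave 5.6-5.8%, 7.7-8.2% and 15.6-17.7%.

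**4. Power of a test that allows for s.** Power = Φ(b/√(v + s²(1/3 + 1/K)) − 1.96). Three choices of b were used for 24%/21%: log rate ratio (0.470/0.336); log hazard ratio, ln[ln(1−p)/ln(0.85)] (0.524/0.372); and log hazard ratio with uniform accrual over 12 months and constant hazard h, solving p = 1 − (1 − e^−h)/h (0.545/0.385). Entries are power (%) at +9/+6 points over K = 10 to 40.

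| s | Rate ratio | Hazard ratio | Hazard ratio, uniform accrual |
|---|---|---|---|
| 0 | 98.1/80.9 | 99.4/87.9 | 99.7/90.0 |
| 0.05 | 97.3-97.4/77.9-78.4 | 99.1-99.2/85.5-85.9 | 99.4-99.5/87.8-88.2 |
| 0.10 | 94.0-94.8/69.8-71.6 | 97.5-97.9/78.2-79.8 | 98.3-98.6/81.0-82.6 |
| 0.20 | 76.2-80.3/47.5-51.4 | 84.6-88.0/55.5-59.7 | 87.3-90.3/58.4-62.7 |

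Setting power to 98% and 80% and solving for s gives about 0.02-0.03 (rate ratio), 0.09-0.10 (hazard ratio) and 0.105-0.116 (uniform accrual). Replacing 1.96 by the t quantile on K + 1 degrees of freedom (2.20 at K = 10, 2.02 at K = 40) gives, at s = 0.10, 91-94%/61-70% (rate ratio) and 96-98%/70-78% (hazard ratio).

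**5. CUHCC.** If the 1,130 already covers three clinics, CUHCC is counted and adds nothing further. If it covers two equal clinics and CUHCC adds a third (1,130 × 3/2 = 1,695, assumed), the formula in step 1 gives 99.6%/90.1%, and that reason would hold under independence.

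**The case against.** The strongest reply is that the planned model is a Cox model, so the hazard-ratio scale is the relevant one. There the stated figures have slack: with uniform accrual, which section 5.1 itself assumes, 98% and 80% survive to s of about 0.11. That stands for a normal critical value. It does not make the figures conservative, because s is unknown and three intervention clinics call for a small-cluster critical value, which reduces the slack.

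It is also true that the documents give no s and no number of control clinics, that section 5.1 discloses the independence assumption, and that section 5.3.2 says validity depends on secular trends acting equally on both groups of clinics. The power losses are therefore ranges, not estimates. But equal trends between the two groups on average is a different condition from no scatter among clinics within a group, and only the latter justifies the planned standard errors.

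Three stronger readings are tempting, and the documents support none of them:
- **The 98% and 80% are miscalculated, or the study is underpowered.** The figures reproduce, and the loss depends on an s that is not given.
- **Overlap reduces power.** As a statement about variance, the plan is right in direction; only the size is small. In the gamma-frailty simulation with full overlap the estimate also shrank at 21% (0.374 to 0.348 at frailty variance 1, 0.377 to 0.334 at variance 3) and net power fell. That shows a net gain is not assured under one assumed structure, not that overlap does harm here.
- **The type I error is 8%.** It exceeds 5% only if s is above zero, and 8% belongs to s = 0.10.

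**Conclusion.** The concern holds in two parts. The more important is the analysis. With three intervention clinics, no clinic term, and robust errors described only for repeat women, the primary test rejects too often whenever clinics differ in their pre-to-post change: about 6%, 8% and 16-18% at s = 0.05, 0.10 and 0.20.

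The lesser part is the wording of the power section. The arithmetic is sound under independence, but neither reason given makes it conservative. Overlap is worth a few points at most at +6 and under one point at +9, and CUHCC counts only if it lies outside the 1,130, which the text contradicts. Clinic variation works the other way, and how soon it brings power below the stated figures depends on the scale.

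This rests on assumed 10 to 40 control clinics, equal clinic sizes, two-sided 0.05 and a range for s. Unequal intervention clinics would make it somewhat worse: a 50/30/20 split raises the factor 1/3 to 0.25 + 0.09 + 0.04 = 0.38. The point about no pre-period event applies to completed screening; for the secondary outcome, a woman could have initiated screening without completing it.

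**What to change.** In section 5.3.2, add clinic-level inference with a small-cluster correction, weighted by the information each clinic contributes, alongside the planned robust errors for repeat women. At a minimum, make it a pre-specified sensitivity analysis that qualifies the primary p-value. An unweighted permutation of clinic changes is not a good choice. In a simulation with equal clinics and no clinic variation (1,500 runs), its power at +9/+6 points was about 93%/68% with 10 control clinics, 81%/44% with 20 and 48%/14% with 40, because small control clinics have noisy changes.

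In section 5.1, replace the claim of conservatism with a statement that 98% and 80% assume independent data with no clinic-by-period variation, and that the gain from overlap is expected to be small. Name the scale and alpha, show power over a range of s (for example 0.05 to 0.20, with s defined as the SD of the clinic-level change), and state whether the 1,130 includes CUHCC.

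The cost is a short recalculation and a few sentences, wider confidence intervals and less favourable stated power. No extra patients or data are needed.
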